4. MATERIALS AND METHODS

The present study will be characterized as a randomized, double-blind, placebo-controlled clinical trial. The sample calculation was based on the current prevalence of ASD in children according to the latest release from the Center for Disease Control, with a target of 270 volunteer participants with ASD, maintaining a confidence interval of 5%.

Pre-screening will have immediate action, and volunteers can register by filling out a virtual recruitment questionnaire available on the website www.gon1.com.br. This phase is crucial in raising sponsorship funds to ensure the feasibility of the research, considering the minimum sample safety requirements. It is emphasized that the analysis of inclusion criteria and contact with families will only be conducted after the project approval by this Research Ethics Committee.

The safety of using the probiotic mix will be ensured by the results obtained from toxicity and pathogenicity tests and by defining the supplement ceiling (zinc 20% 0.148g, selenium 1% 0.032g + magnesium 65mg + vitamin A 0.300g) contained in the K11-Tmax version according to the positive list from ANVISA stratified at the age of 3 years.

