4.1. SAMPLE SELECTION

Inclusion Criteria:

- Volunteers must have a confirmed diagnosis of ASD conducted by qualified professionals, according to the criteria established in the Diagnostic and Statistical Manual of Mental Disorders (DSM-5) or another recognized diagnostic classification.
- The study will include children and adolescents in the specific age range of 3 to 11 years.
- Must be regularly enrolled in a public or private school, or in a special education center.
- Absence of uncompensated clinical or psychiatric comorbidities.
- Informed consent: Legal guardians must provide informed consent, understanding the study objectives, procedures involved, risks and benefits, as well as the freedom to withdraw from the study at any time.
- Informed assent: Children aged 7 to 11 years must provide informed assent, understanding the study objectives, procedures involved, risks and benefits, as well as the freedom to withdraw from the study at any time.

Exclusion Criteria:

- Concomitant restrictive medical conditions that may interfere with study results, such as severe gastrointestinal diseases, significant metabolic diseases, or immunodeficiencies.
- Use of specific medications such as broad-spectrum antibiotics or immunosuppressive drugs during the follow-up period.
- Allergies or intolerances to components of the probiotics that will be administered.
- Previous or current participation in recent clinical studies with distinct therapeutic interventions.
- Uncontrolled cardiac conditions or severe unstable medical illnesses.
- Inability to be present on the predetermined dates of clinical assessments.

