4.2. EXPERIMENTAL PROTOCOL

4.2.1. Study Design

This study will be conducted in a medical clinical specifically adapted for testing and with a permissive playful space to mitigate the stress of the involved children and avoid social conflicts during evaluation sessions. The space will comprise at least 17 individual analysis rooms, and the evaluation will involve 20 neuropsychologists, 2 pediatricians and 1 psychiatrist with prior and ensured training.

Children will be evaluated on DAY 0, DAY 45 and DAY 90 to quantify inflammatory markers through blood collection; for measuring fecal calprotectin, by collecting fecal samples; and finally, for the primary outcomes mentioned in this project: neuropsychological (Vineland-3); psychiatric (ADOS) and psychopedagogical (CARS). After the first data collection, individuals will be randomized to receive the K11-T probiotic mixture or the K11-Tmax probiotic mixture or placebo, in a 1:1:1 ratio. After the initial 90-day follow-up, up to 30% of the sample using K11-Tmax will continue to be monitored, being re-evaluated after 365 days in all aspects mentioned. Children will be stratified by age, gender and level of support (see Appendix B) and then randomized to intervention according to the groups below.

Condition or Disease	Intervention/Treatment	Phase
Children with ASD	Drug 1: Probiotic K11-T Drug 2: Probiotic K11-Tmax Drug 3: Placebo	Phase 3

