4.2.8. Neuropsychological Assessment

Neuropsychological assessment in patients with ASD involves a multidisciplinary approach, considering different aspects of neuropsychological functioning. Standardized analysis will be

conducted using the Vineland Adaptive Behavior Scales - Third Edition (Vineland-3)⁴⁶. The forms will be completed in their self-administered version by parents/caregivers and teachers, under the supervision of a qualified and trained health professional. Vineland-3 assesses adaptive behavior by dividing it into five domains: communication skills, daily living skills, socialization skills, motor skills and maladaptive/behavioral skills of the child. Those responsible will respond to the items in each domain on a scale ranging from 0 to 2, with 0 being never; 1 sometimes and 2 often. To calculate the final score, the scores are transformed into a population average of 100 based on age and a standard deviation of 15 according to the specific and standardized manual for the scale. A higher score indicates greater adaptive functioning.

The Vineland-3 is clinically validated for use in tracking change over time⁴⁷ and is used as an outcome measure in several randomized controlled trials for children with ASD.⁴⁸

It should be noted that the adaptive scale in question is a specific neuropsychological battery, and its content must be acquired for individual application. Therefore, its independent disclosure or copying for any purpose is prohibited. Therefore, it is not possible to include it in its entirety in this project.

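### The target of 270 rests on the population prevalence of ASD and an undefined 5% confidence interval, which is not a valid basis for comparing three arms of children who all have ASD

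*Protocol*

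**What the plan says.** Protocol section 4 (Materials and Methods) gives the only stated basis for the sample size: "The sample calculation was based on the current prevalence of ASD in children according to the latest release from the Center for Disease Control". The same sentence then sets the number and its supposed precision: "with a target of 270 volunteer participants with ASD, maintaining a confidence interval of 5" per cent. It gives no prevalence value, does not say what the 5% refers to, and names no treatment difference, SD or power.

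The design that this number serves is set out elsewhere:

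- Section 4.1 requires the disorder at entry: "Volunteers must have a confirmed diagnosis of ASD conducted by qualified professionals".
- Section 4.2.1 fixes the allocation: "individuals will be randomized to receive the K11-T probiotic mixture or the K11-Tmax probiotic mixture or placebo, in a 1:1:1 ratio". It also fixes the outcomes: "for the primary outcomes mentioned in this project: neuropsychological (Vineland-3); psychiatric (ADOS) and psychopedagogical (CARS"). And it fixes the visits: "Children will be evaluated on DAY 0, DAY 45 and DAY 90".
- Section 4.2.11 (Biostatistics) compares groups by t-test, ANOVA, repeated measures or non-parametric counterparts, at a 0.05 significance level.

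Section 4.2.7 reuses the total (30% of 270 is 81) but does not justify it.

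**The concern.** A prevalence sizes a survey that estimates a proportion. This trial estimates no prevalence: ASD is present in 100% of participants by design, and the question is whether mean scale scores differ between arms. How common ASD is in the population does not enter the variance, the effect or the power of any such comparison.

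The 5% is also open to more than one reading, for instance a 5-point margin of error or a 5% significance level. A confidence interval is not described by a single percentage.

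As a result, the stated calculation does not say what treatment difference, or what precision, 270 children are meant to deliver. An ethics committee cannot judge from it whether 90 children per arm fits the objectives, and a null result could not be read against any stated target.

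**Working it through.** **1. Trying to reproduce 270 from the stated basis.** The standard formula that uses a prevalence p and a margin d is n = z² p(1 − p)/d². Take z = 1.96 (95% confidence) and read the 5% as d = 0.05. The protocol gives no p, so a range is assumed.

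| Assumed p | n |
|---|---|
| 0.5% | 8 |
| 1% | 16 |
| 3% | 45 |
| 5% | 73 |

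Reading n as a number per arm and multiplying by three gives 24 to 219. To reach 270 in total, p would have to be about 22.7%: 1.96² × 0.227 × 0.773/0.0025 ≈ 270. Other readings come close only with inputs that the protocol does not state, for example 90% confidence with p = 50% (271). So 270 cannot be reproduced from what is written. Even if it could be, the result would be the precision of a proportion, not of a difference between arms.

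**2. What 270 delivers for the comparison actually planned.** Inputs from the protocol: N = 270, three arms at 1:1:1, so 270/3 = 90 per arm; alpha 0.05 (section 4.2.11), taken as two-sided. Assumed: 80% power, and one active arm against placebo on one outcome at one visit, with no baseline adjustment, dropout or multiplicity correction.

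- Standard error of the difference in SD units: √(2/90) = 0.149.
- Normal approximation: (1.960 + 0.842) × 0.149 = 0.418. With the noncentral t on 178 df, the detectable difference is **0.420 SD**.
- Expected 95% CI half-width: 1.973 × 0.149 = **0.294 SD**.
- Power at a true difference of 0.3 SD: 52%.

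The only SD in the protocol is the Vineland-3 norm (section 4.2.8: "the scores are transformed into a population average of 100 based on age and a standard deviation of 15"). If it applied to these children, 0.42 × 15 = 6.3 points. It is a population norm and may not be the SD in children with ASD.

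**3. How far the figure moves.** Baseline adjustment multiplies the residual SD by √(1 − r²), where r is the baseline correlation (assumed; the protocol gives none). An assumed 15% loss leaves 76 per arm (90 × 0.85 = 76.5). Multiplicity is illustrated by dividing alpha by 3 (three pairwise comparisons, or three outcomes) or by 9 (both).

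| Case (80% power) | Detectable difference, SD |
|---|---|
| Unadjusted, no loss, alpha 0.05 | 0.42 |
| Baseline adjusted, r = 0.5 / 0.7 / 0.8 | 0.36 / 0.30 / 0.25 |
| 15% loss, unadjusted | 0.46 |
| Alpha 0.05/3, unadjusted, no loss | 0.49 |
| Alpha 0.05/9, unadjusted, no loss | 0.54 |

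Power at 0.3 SD rises from 52% to 64%, 80% or 92% at r = 0.5, 0.7 or 0.8. So 0.42 SD is conservative only with respect to baseline adjustment. It is optimistic with respect to dropout and multiplicity.

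**The case against.** The strongest reply is that no harm to the trial has been shown. There is no bias and no demonstrated shortfall, and 90 per arm is a respectable size. That is right, and it limits the point to a defect of justification. A reader might infer that 270 is too small. The protocol does not support that, because it states no target difference, and power at 0.3 SD ranges from 52% to 92% on assumed correlations alone.

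A second reply is that the missing prevalence sits in a cited source, and that the 5% is probably loose wording for the significance level in section 4.2.11. Both may be so. The point does not rest on reproducibility or on that phrase: supplying the prevalence, or rewording the 5%, would leave prevalence as the basis.

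A third is that details can wait for a statistical analysis plan. But the protocol does not merely omit a calculation. It asserts one on the wrong parameter, and a later document would not make that sentence correct.

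A reader might also infer that feasibility really set the number, since section 4 says of pre-screening: "This phase is crucial in raising sponsorship funds to ensure the feasibility of the research, considering the minimum sample safety requirements", and section 6 mentions a minimum sample for the investor. Those sentences concern pre-registration and funding. Neither ties feasibility to 270, and section 4 names prevalence as the basis.

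**Conclusion.** The concern holds as a defect in the stated justification. Population prevalence and an undefined 5% confidence interval are not a valid basis for sizing a three-arm comparison of scale scores in children who all have ASD, and no other section supplies a different basis.

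Whether 270 is adequate remains open. It turns on the target difference, the baseline correlation, the dropout and the multiplicity rule, none of which the stated rationale contains. The 0.42 SD figure assumes two-sided alpha 0.05, 80% power, a single pairwise comparison on one outcome at one visit, and complete data. The correlations, the 15% loss and the divided alphas are illustrations, not figures from the protocol.

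**What to change.** In section 4, delete the prevalence and confidence-interval rationale. Name the comparison and the primary outcome that the size is meant to serve, and state what the planned size delivers. Suggested wording:

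> The target is 270 children, 90 per arm. For one active arm versus placebo on one outcome at one visit, without baseline adjustment and before dropout and multiplicity adjustment, 90 per arm give 80% power at two-sided alpha 0.05 for a standardised difference of 0.42 (expected 95% CI half-width 0.29 SD).

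Then restate the figure for the baseline adjustment, dropout and multiplicity rule actually planned, and say whether the team considers that difference relevant. Without that last statement the sentence describes the size but does not justify it. Label any conversion to Vineland-3 points as assuming the norm SD of 15.

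The cost is one paragraph of wording, with no extra children and no change to arms, outcomes or analysis. The downside is a less favourable stated justification: if the team's target difference is smaller than the size can detect, that becomes visible. A 0.3 SD target, for instance, needs 176 per arm unadjusted, or 132, 90 or 64 at an assumed baseline correlation of 0.5, 0.7 or 0.8.

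### No visit in the protocol records clinical adverse events, so the three arms could be compared on effect measures but not on clinical harms

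*Protocol*

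**What the plan says.** Section 4 (Materials and Methods) gives the protocol's only stated basis for safety: "The safety of using the probiotic mix will be ensured by the results obtained from toxicity and pathogenicity tests", together with a ceiling on the supplements "contained in the K11-Tmax version according to the positive list from ANVISA stratified at the age of 3 years". No test is named, and no species, population, date or citation is given. The ceiling applies to K11-Tmax, so for K11-T the test results are the only stated basis.

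The population is fixed in section 4.1: "The study will include children and adolescents in the specific age range of 3 to 11 years". The design is fixed in section 4: "The present study will be characterized as a randomized, double-blind, placebo-controlled clinical trial". The table in 4.2.1 labels the trial Phase 3.

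Section 4.2.1 sets the visit content: "Children will be evaluated on DAY 0, DAY 45 and DAY 90 to quantify inflammatory markers through blood collection", then stool samples for calprotectin, then visits "for the primary outcomes mentioned in this project: neuropsychological (Vineland-3); psychiatric (ADOS) and psychopedagogical (CARS". For the extension, "up to 30% of the sample using K11-Tmax will continue to be monitored, being re-evaluated after 365 days in all aspects mentioned". No placebo or K11-T children are named for that follow-up.

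**The concern.** Test results and a composition limit can support starting a trial. They cannot establish what happens to children with ASD who take one dose a day for 90 days, so the claim that safety is ensured goes further than its basis allows. The claim would matter less if the visits recorded adverse events, but the text describes no such recording.

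A separate analysis plan could not repair this. What families are asked, when and by whom is visit content, which the protocol fixes, and an analysis plan cannot tabulate data that no visit collects.

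At stake is the weighing of benefit against harm. The trial could report an improvement on Vineland-3, ADOS or CARS with no systematic record of gastrointestinal upset, rash, infection or hospital admission to set beside it. Randomisation, blinding and placebo would be in place, but they would not be used for that comparison.

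**Working it through.** **Step 1: search for a place where adverse events could be recorded.** The protocol states no safety figure to reproduce, so the check is a reading of each section.

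| Section | Content relevant here | Adverse-event item |
|---|---|---|
| 2 and 3, objectives | Effectiveness and inflammatory markers | None |
| 4.2.1, visits | Blood markers, stool, Vineland-3, ADOS, CARS. Two pediatricians on the team, no safety task given | None |
| 4.2.3 to 4.2.7, laboratory | CRP, cortisol, insulin, prolactin, calprotectin | None |
| 4.2.8 to 4.2.10, scales | Vineland-3, ADOS-2, CARS | None |
| 4.2.11, biostatistics | Tests for the research variables | None |
| 6, schedule | Includes a questionnaire row in April, May and July, content not given | None stated |
| 7, costs | Includes lines for volunteer support and biochemical tests, content not given | None stated |
| Annex A, form | Identity, support level, randomisation code, comorbidities | None |

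**Step 2: size of the groups.** The target is 270 (section 4) and allocation is 1:1:1 (section 4.2.1). That gives 270 / 3 = 90 per arm and 180 on an active product. The extension covers up to 0.30 × 90 = 27 K11-Tmax children.

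**Step 3: what collection would give at this size.** The protocol gives no event rates, so the rates below are assumptions, shown as a range. Full retention is assumed throughout.

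*Upper limit when no event of a type is seen in an arm of n = 90.* One-sided 95% limit: 1 − 0.05^(1/90) = 0.0327, or 3.3%. The upper end of a two-sided 95% interval is 1 − 0.025^(1/90) = 0.0402, or 4.0%.

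*Chance of seeing at least one event in an arm,* 1 − (1 − r)^90: for r = 1%, 59.5%; for r = 2%, 83.8%; for r = 5%, 99.0%.

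*Power, one active arm against placebo,* two-sided 5% (the protocol gives 0.05 without stating sidedness). With p̄ the mean of the two rates, z = [|p₂ − p₁|√90 − 1.96√(2p̄(1 − p̄))] / √(p₁(1 − p₁) + p₂(1 − p₂)), and power = Φ(z). For 5% vs 20%: (1.423 − 0.917) / 0.456 = 1.11, so power is 87%.

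| Placebo rate | Active rate | Power |
|---|---|---|
| 5% | 10% | 25% |
| 5% | 15% | 61% |
| 5% | 20% | 87% |
| 10% | 20% | 47% |
| 10% | 30% | 93% |

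**Step 4: as written.** With no recording described, none of these limits or comparisons would be obtained.

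**The case against.** The strongest reply is that the section 4 sentence is about the product. It does not say that adverse events will go unrecorded, and the rest of the argument is from silence. The consent pages are not in the text reviewed, and they may tell families how to report problems. The questionnaire row in section 6 recurs in the same months as the assessments and is not defined, and two cost lines in section 7 are equally open. This stands as a limit on wording: the point is that no recording is described in the text shown, not that the sponsor has decided against it. It does not remove the point. The only general participant questionnaire described is the sociodemographic one in section 3, and spontaneous reports from families are not the same question asked equally in every arm.

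A reader might infer that the trial gives no safety information at all and that any harm would go unseen. The protocol does not support that. Serum markers are measured at Days 0, 45 and 90. Vineland-3 has a maladaptive domain, and ADOS covers atypical behaviours. A harmful shift in any of these could be seen by arm. However, section 3 sets them up as effect measures, calprotectin is a convenience subsample of at least 81 children, and none of them records a clinical event.

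A reader might also infer that the toxicity tests were completed before the trial. The protocol gives no date for them.

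Finally, the 3.3% limit is generic to any arm of 90 and bounds a rate in one arm, not a difference. That is fair, which is why the power figures are shown beside it, and they are modest.

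**Conclusion.** The point holds in this form. The protocol text shown describes no recording of clinical adverse events at any visit. It rests safety in children aged 3 to 11 on unnamed, undated test results and on a ceiling that applies to one of the two active products. Followed as written, the trial would show by arm only shifts in its effect measures.

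What would be lost is useful but limited: a 3.3% one-sided upper limit per arm for an event never seen, good power only for large differences, and little power for a doubling from 5% to 10%. These figures rest on 90 per arm, full retention and assumed event rates. The extension is a separate case. It follows K11-Tmax children only, so it could not give a comparison by randomised arm even with recording. No dose, ceiling value or treatment rule is judged here.

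**What to change.** In section 4, say that safety is *supported* by the test results and the supplement ceiling, in place of *ensured*. That edit alone adds no data, so also add to section 4.2.1 that adverse and serious adverse events are asked about with the same standard questions in all three arms at Day 45 and Day 90, by staff blind to arm, and tabulated by randomised arm.

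Use the same form at Day 365, and at T180 if that visit takes place (it appears in the section 7 costs but not in 4.2.1). Report those results descriptively.

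The cost is one short form at visits already planned, with pediatricians already on the team, slightly longer visits and one more table. The change concerns data collection only and sets no stopping or treatment rule.

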4.1. SAMPLE SELECTION

Inclusion Criteria:

- Volunteers must have a confirmed diagnosis of ASD conducted by qualified professionals, according to the criteria established in the Diagnostic and Statistical Manual of Mental Disorders (DSM-5) or another recognized diagnostic classification.
- The study will include children and adolescents in the specific age range of 3 to 11 years.
- Must be regularly enrolled in a public or private school, or in a special education center.
- Absence of uncompensated clinical or psychiatric comorbidities.
- Informed consent: Legal guardians must provide informed consent, understanding the study objectives, procedures involved, risks and benefits, as well as the freedom to withdraw from the study at any time.
- Informed assent: Children aged 7 to 11 years must provide informed assent, understanding the study objectives, procedures involved, risks and benefits, as well as the freedom to withdraw from the study at any time.

Exclusion Criteria:

- Concomitant restrictive medical conditions that may interfere with study results, such as severe gastrointestinal diseases, significant metabolic diseases, or immunodeficiencies.
- Use of specific medications such as broad-spectrum antibiotics or immunosuppressive drugs during the follow-up period.
- Allergies or intolerances to components of the probiotics that will be administered.
- Previous or current participation in recent clinical studies with distinct therapeutic interventions.
- Uncontrolled cardiac conditions or severe unstable medical illnesses.
- Inability to be present on the predetermined dates of clinical assessments.

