4.2.11. Biostatistics

Mean and SD (standard deviation) will be used to describe quantitative data, while risk factors, frequency and percentage will be used to describe qualitative data. Shapiro-Wilk test will confirm or not the normality of data distribution in the groups, therefore, parametric, or non-parametric tests, respectively, will be used to assess the research variables. To compare quantitative variables in the two or more groups, independent t-test (between groups) or paired samples t-test (within groups), ANOVA (between groups) or Repeated Measures (within groups), with post hoc testing to assess individual differences among the categories, will be used as parametric options. The relatives nonparametric options will be used otherwise and chi square test, if qualitative variables. All statistical calculations will be performed at the significance level of less than 0.05 (P < 0.05). Data will be analyzed using SPSS version 26.0.

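### The antibiotic and immunosuppressant exclusion in 4.1 is timed to follow-up, so read literally it excludes randomised children on a post-randomisation event and does not screen use at entry

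*Protocol*

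**What the plan says.** The exclusion criteria in Protocol section 4.1 (Sample Selection) include "Use of specific medications such as broad-spectrum antibiotics or immunosuppressive drugs during the follow-up period". They give no screening date or look-back window for these drugs.

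Section 4.2.1 (Study Design) fixes the timeline. Assessments are on Day 0, Day 45 and Day 90. Allocation, equal across the three arms, comes after the first of these: "After the first data collection, individuals will be randomized to receive the K11-T probiotic mixture or the K11-Tmax probiotic mixture or placebo". The same section identifies the follow-up and a later phase for part of one arm: "After the initial 90-day follow-up, up to 30% of the sample using K11-Tmax will continue to be monitored, being re-evaluated after 365 days".

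Section 4 sets the sample size at 270. Section 4.2.11 (Biostatistics) sets significance at 0.05 and does not say whether children are analysed as randomised. Nothing in the protocol says what happens to a randomised child who starts one of these drugs.

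**The concern.** An eligibility criterion should rest on facts known before allocation. This one names a window that opens after allocation. A child who finishes a broad-spectrum antibiotic just before Day 0 is not caught by it, while a randomised child who starts one on Day 30 is.

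If staff follow the wording, they may stop assessing such children, and the Day 45 and Day 90 values are then never collected. The arms are compared on whoever did not need the drugs. At the least this loses precision on the three primary scales (Vineland-3, ADOS, CARS). If use of the drugs differs by arm and users differ in outcome, it also biases the comparison. Section 5 rests the trial on probiotics acting on the microbiota, inflammation and gastrointestinal health, so a difference in use is plausible, but the protocol does not state one.

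**Working it through.** **Timing.** Section 4.2.1 gives the order: Day 0 collection, randomisation, 90-day follow-up with visits at Day 45 and Day 90. The criterion in 4.1 refers to the last of these. At enrolment one can know current long-term use and use already scheduled. A drug started later for a new illness cannot be known.

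**Inputs from the protocol.** 270 children at 1:1:1 give 270/3 = 90 per arm; alpha is 0.05. The protocol does not state sidedness, power, rates of drug use or outcome differences between users and non-users. I assume a two-sided test, 80% power and the rates shown below. The protocol gives no figure on this point to reproduce.

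**Precision, equal use in both arms.** The detectable difference between two arms in SD units is (1.960 + 0.842) × √(2/n) = 2.802 × √(2/n).
- No exclusion, n = 90: 2.802 × √(2/90) = 0.42.
- 10% excluded, n = 81: 0.44. Power for a difference of 0.418 SD falls from 80% to about 76%.
- 20% excluded, n = 72: 2.802 × √(2/72) = 0.47. Power falls to about 71%.
- 30% excluded, n = 63: 0.50. Power falls to about 65%.

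Using the t distribution instead gives 0.420 at n = 90 and 0.470 at n = 72. With equal rates and the same mechanism in each arm there is no bias.

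**Bias, unequal use, simple model.** Let non-users have the same mean in both arms and let users score d SD worse. An arm with a proportion p of users then has a mean p × d below its non-users. Among all randomised children the probiotic arm is better by (p_placebo − p_probiotic) × d. After users are excluded the contrast is zero. Exclusion therefore shifts the result against the probiotic by that product. With probiotic use set at half of placebo use:
- 20% against 10%, d = 0.5: (0.20 − 0.10) × 0.5 = 0.05 SD.
- 30% against 15%, d = 1.0: (0.30 − 0.15) × 1.0 = 0.15 SD.

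The upper value is 0.15/0.42 = 36% of the detectable difference.

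**Bias, second model as a check.** Assume no treatment effect on outcome and a normally distributed tendency to use the drugs that correlates ρ with worse outcome. Excluding the top proportion p improves the mean of those retained by ρ × φ(z)/(1 − p), where φ is the standard normal density and z the (1 − p) quantile. The difference between arms is the bias, again against the probiotic. For ρ from 0.3 to 0.5:
- 10% against 5%: 0.03 to 0.04 SD; two-sided type I error 5.3% to 5.9%.
- 20% against 10%: 0.05 to 0.08 SD; 5.9% to 7.7%.
- 30% against 15%: 0.07 to 0.11 SD; 6.8% to 10%.

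In both models the placebo arm loses more of its worse-scoring children and looks better than it should. If use were higher on probiotic, or if users scored better, the sign would reverse.

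**The case against.** The criterion stands in a selection list beside items judged at entry, such as allergies and earlier trial participation. In that setting it may simply mean expected use, and maintenance immunosuppression or scheduled antibiotics can be established at screening. No section says that a randomised child who starts such a drug is withdrawn or left out of the analysis. Where the protocol does discard data it says so, as for certain stool samples in 4.2.7. Analysis sets are commonly left to a statistical analysis plan, which is not at hand. No effect of the product on infections or prescribing is claimed, and every rate used above is assumed.

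Much of this stands. It would be too strong to say that the criterion can act only on randomised children, or that the protocol orders their removal from the analysis. The magnitudes are illustrations.

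It does not remove the point. The text says use, not planned use, and its only time reference lies after randomisation. Even if expected use was meant, use at entry goes unscreened and the wording needs correcting. An analysis plan can define who is analysed, but it cannot recover visits that were not made because a child was treated as excluded.

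**Conclusion.** The criterion is badly timed and should be reworded; my confidence is medium, because the step from the wording to actual removal is inferred. Applied literally, it costs precision in any case: from 0.42 to 0.47 SD detectable at an assumed 20% use per arm. It adds bias only if use differs by arm and users differ in outcome. Under the stated assumptions that bias is 0.05 to 0.15 SD in the simple model and 0.03 to 0.11 SD in the second, against the probiotic.

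A reader might infer three stronger things that the protocol does not support:
- That the randomised comparison is broken for all primary scales. This needs application after randomisation, removal from analysis and a difference between arms, none of which is stated.
- That the error would favour the product. In the scenarios worked here it runs the other way.
- That the attendance criterion, "Inability to be present on the predetermined dates of clinical assessments", has the same fault. The dates are fixed in advance, so it reads naturally as a question put to families at screening.

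**What to change.** In 4.1, reword the criterion so that it is judged at screening only: current use, or use already planned at enrolment, with the look-back window set by the investigator. Add that use starting after randomisation is recorded with dates, and that the child remains in follow-up and is analysed in the randomised arm. An analysis without such children may be given as a sensitivity analysis. Clinical handling of these children is for the sponsor to settle.

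The cost is about two sentences in 4.1 and one concomitant-medication field on the case report form. The small downside is that some analysed children will have used these drugs, which may dilute the effect slightly.
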